Study Title: Phono- and Electrocardiogram Assisted Detection of Valvular Disease

NCT Number: Pending

UCSF CHR Number: 17-21881

Date: 3/1/18

Study Protocol and Statistical Analysis Plan

Phono- and Electrocardiogram Assisted Detection of Valvular Disease (PEA-Valve Study)

Investigator team: [name], [name], [name], [Study coordinator to be named], [[name]/[name]]

Abstract

The diagnosis of valvular heart disease (VHD), or its absence, invariably requires cardiac imaging. A familiar and inexpensive tool to assist in the diagnosis or exclusion of significant VHD could both expedite access to life-saving therapies and reduce the need for costly testing. The FDA-approved Eko Duo device consists of a digital stethoscope and a single-lead electrocardiogram (ECG), which wirelessly pairs with the Eko Mobile application to allow for simultaneous recording and visualization of phono- and electrocardiograms. These features uniquely situate this device to accumulate large sets of auscultatory data on patients both with and without VHD.

In this study, we seek to develop an automated system to identify VHD by phono- and electrocardiogram. Specifically, we will ask whether we can develop machine learning algorithms to learn the phonocardiograms of patients with clinically important aortic stenosis (AS) or mitral regurgitation (MR), and then task the algorithms to identify subjects with clinically important VHD, as identified by a gold standard, from naïve phonocardiograms. We anticipate that our study has the potential to revolutionize the diagnosis of VHD by providing a more accurate substitute to traditional auscultation.

Specific aim(s)

Aim 1: Can a machine learning algorithm derived from simultaneous phono- and electrocardiogram recordings reliably diagnose clinically important aortic stenosis?

Aim 2: Can a machine learning algorithm derived from simultaneous phono- and electrocardiogram recordings reliably diagnose clinically important mitral regurgitation?

Significance

Valvular heart disease (VHD) is a common global health problem, with population-based studies showing a prevalence of 10% for aortic stenosis (AS) and 20% for mitral regurgitation (MR).^{1,2} New surgical and interventional advances allow us to treat patients at an older age or whose risk of intervention would previously have been untenable.³ Given that the incidence of both MR and AS increases with increasing age, there is a growing need to identify these conditions so as to offer disease-altering therapies.

In current clinical practice, the diagnosis of VHD relies heavily on echocardiography.⁴ This, in turn, requires both a referral from a provider with a clinical suspicion for VHD, typically from an abnormality on auscultation, as well as access to the echocardiogram itself. MR and AS both result in reliably reproducible auscultatory findings: holosystolic and systolic crescendo-decrescendo murmurs, respectively.⁵ Yet despite this, auscultation as a diagnostic tool is notoriously poor: its accuracy to detect MR and AS ranges only from 5-40%.^{6,7} These factors all lead to concerns for underdiagnosis of these increasingly treatable conditions.

Here, we will address the needs for both greater access to and improved diagnostic accuracy of testing for VHD. We will utilize a combination of phonocardiogram (PCG) and single-lead electrocardiogram (ECG) recordings, synced in real-time to a secure cloud-based server, using the Eko Duo electronic stethoscope. With these data, we will develop and validate a machine learning algorithm to diagnose clinically important AS or MR. As the Eko Duo is essentially similar to a traditional stethoscope, an iconic tool widely accepted by patients and providers alike, its use to drive an automated detection algorithm is both feasible and attractive as a substitute for traditional auscultation. Furthermore, by shifting the burden of test interpretation away from the clinician and onto the algorithm, we hypothesize that we will improve overall diagnostic accuracy.

Methods

Overview of design: Cross-sectional study of all subjects undergoing clinical echocardiograms at the UCSF adult echocardiography laboratory

Study subjects

Overview: We will enroll adult subjects undergoing clinical echocardiograms at the UCSF Parnassus campus. These subjects will be grouped into derivation and validation cohorts sequentially, stratified by case status, so as to reach the expected sample size. Such grouping will occur after subject enrollment and data collection.

Target Population: Adults with either moderate-to-severe to severe AS or moderate-to-severe to severe MR (cases) and adults with structurally normal hearts with minimal VHD (controls). In a more-stringent, parallel analysis, a target population of controls will be defined as having any degree of AS or MR less than moderate-to-severe.

Accessible Population: Adults meeting the entry criteria undergoing clinical echocardiograms at the UCSF echocardiography laboratory amenable to participation.

Inclusion Criteria:

- Adults > 18 years of age
- Able to provide consent
- Undergoing complete (i.e. not limited) echocardiogram studies

Exclusion Criteria:

- Refusal to participate

Sampling Scheme: We will approach subjects presenting to the adult echocardiography laboratory at UCSF Parnassus consecutively. Additionally, we will pre-screen subjects for a high likelihood of having AS or MR (based on indication for study and prior diagnoses in the APEX medical record) and selectively their enrollment during situations where the enrollment capacity of the study coordinator is saturated.

Recruitment Strategy: Introduction of study at time of registering for echocardiogram with a brochure or flyer, followed by in-person approaching of potential subjects while awaiting the clinical echocardiogram.

Retention Strategy: None. We will retain a master file of the medical record numbers to identify contact information in the future if deemed necessary.

Measurements

Overview: Our study will focus on two measurements: 1) the gold standard assessment of VHD by echocardiogram, as reported by the UCSF echocardiography laboratory. 2) 10 second simultaneous PCG and single-lead ECG recordings by the Eko Duo device at each of the four standard cardiac auscultatory positions. Our study takes advantage of the fact that all clinical echocardiogram reports include these valvular assessments.

Gold Standard: The echocardiogram is accepted as the gold standard for diagnosis of VHD severity by the cardiology community.⁴ To minimize the burden on the investigators, as well as reduce costs, we will take advantage of that all clinical echocardiogram reports include assessments of VHD, which will serve as our gold standard. These reports follow American Society for Echocardiography (ASE) guidelines,^{8,9} which allow grading of VHD as follows: none, mild, moderate, or severe. The UCSF echocardiography laboratory includes additional categories of trace, mild-to-moderate, moderate-to-severe, and critical, allowing for interpretations where individual parameters within the study conflict. Our primary measurement will be the final conclusion of severity of VHD for MR or AS, as reported by a board-certified cardiologist. We will define “clinically important” VHD as that graded moderate-to-severe or worse, as this would encompass all levels of disease which could require direct intervention. In addition, we will extract the entire echocardiography report, as well as the images of the echocardiogram files, so as to save the data for future use as new research questions arise.

Device Measurements: Recordings of the simultaneous PCG and single-lead ECG will be performed for each subject in a standardized manner. Each subject will undergo 10 second recordings using the Eko Duo device at the four standard auscultation positions. Observers will be trained on the systematic method of obtaining measurements. Time and patient permitting, we will also obtain the same recordings using the Eko Core device, which uses the same software but does not include ECG recording. As the device will allow visualization of the PCG during recording, the observer will get real-time feedback on positioning of the device to maximize the quality of the recording at each position. We will plan for periodic review of recordings to ensure adequate data quality. We anticipate that this flexibility and real-time feedback will improve the generalizability of the use of the device to a real-world (i.e. non-study) clinical situation.

Primary Outcome: Our primary outcome will be the identification of either clinically important MR or AS (either present or absent) by the algorithm on the device measurements from subjects in the validation set. For the primary outcome, we will define our controls as patients with VHD no greater than mild severity as per the gold standard. As our algorithm will provide a score comparing similarity of the learned characteristics with test (validation set) data, we will plot our results as a receiver operating characteristic (ROC) curve at each score. In addition, we will plan to calculate

the likelihood ratios (both positive and negative) of the test at sensitivity cutoffs of 0.9, 0.95, and 0.99.

Secondary Outcome: Our secondary outcome will be substantially the same as our primary outcome, but in this case, we will define our controls as all subjects with less than moderate-to-severe or greater disease of the valvular condition (MR or AS) in question. This will necessitate the generation of a separate algorithm with the derivation set, which we will perform in parallel.

Confounders and Bias: The derivation and validation of our algorithms will occur remotely, after the clinical echocardiogram has been performed, and therefore with no effect on the outcome of the gold standard. Our test may be influenced by the presence of other conditions causing systolic murmurs (including VHD other than AS or MR, or congenital heart disease). We will include these measures from the echocardiogram report to compare test performance in those with and without these other conditions.

Statistical issues

Null Hypothesis: A machine learning algorithm cannot predict the presence of clinically important AS or MR.

Sample Size Justification:

- Sensitivity of Algorithm: 90%
- Specificity of Algorithm: 90%
- Target Likelihood Ratio (+) of Algorithm [LR(R)]: 9 (derived from $Sn / [1 - Sp]$)
- Minimum Likelihood Ratio (+) of Algorithm [LR(R)]: 5
- Confidence Level = 0.95 (α = 0.05)
- Confidence Interval [LR(R)]: 5.120-15.820
- Sample Size = 110 per group; 330 per cohort (control, AS case, MR case); 660 overall (training and validation cohorts)
- Summary: Assuming the sensitivity and specificity of the machine learning algorithm for detection of clinically important AS or MR are both 0.9, a total sample size of 660 is not expected to go below the threshold likelihood ratio of 5.0 in the 95% confidence interval in either the derivation or validation cohorts.
- Justification of Critical Assumptions: We assume that our algorithm can produce a sensitivity and specificity of 90% in detecting aortic stenosis or mitral regurgitation compared to hearts with no valvular disease, based upon prior published reports using neural networks, using sample sizes of under 100 cases.¹⁰ Furthermore, we estimate a minimum likelihood ratio of 5 would be necessary for the test to be clinically useful. While this estimate works well for our validation set, the number needed for our derivation set is less clear; the estimates above are a conservative number. We anticipate training the algorithm after enrollment of every 20 cases using a bootstrapping approach; this will provide interim test characteristics and help determine the true number needed for the derivation set. As this is, in part, a pilot study, identification of the true sensitivity and specificity of the test is in itself a valuable result.

Analysis approach: We will generate ROC curves (plotting Sn vs. 1-Sp) for algorithm scores for the validation set. Ultimately we will generate 4 curves: two each for MR and AS, using algorithms generated by our primary (defining controls as having no greater than mild VHD) and secondary (defining controls as not having moderate-to-severe or greater VHD) approaches. Additionally, we anticipate performing exploratory, descriptive analyses of the algorithm itself, by identifying clinical correlates to the characteristics most heavily weighted in detecting AS or MR.

Miscellaneous

Ethical considerations: No major concerns. Data will be securely stored on HIPAA compliant platforms. The study qualifies as minimal risk by UCSF CHR criteria.

Pretest plans: Prior to study recruitment, study staff will collect data on themselves and providers to test the data collection system. During initial subject recruitment, study staff will review the process after each day to discuss roadblocks or concerns.

Data Management Plan: Data from our study will come from two sources. Reports of echocardiograms, extracted from the electronic medical record (APEX), will be reviewed by study staff to generate our main database of disease characteristics. A master file linking subject identifiers with identifiable information, as well as extracted and de-identified echocardiogram reports and de-identified raw echocardiogram images will be stored on a secure research server used by the Division of Cardiology. Recorded PCG and ECG data (the actual study measurements) will be synced in real-time to a secure, HIPAA-compliant, cloud-based server managed by Eko Devices. At pre-specified times of algorithm training, the machine learning team (coordinated by Eko Devices) will be provided keys to the assignment of subject identifier to VHD category.

Quality control measures: Periodic review of the recorded data will be performed by the study PI to ensure appropriate data quality.

Timetable:

Contract/Logistics	Subject Enrollment	Algorithm Development	Analysis	Publication
Overall Timetable: 9 Months				

Budget:

Item	Estimated Cost	Notes
Research Coordinator	\$88000	Costs not included: Eko Duo & Eko Core Device
PI (10% FTE)	\$25000	
Statistician (10% FTE)	\$20000	Salary support for machine learning (headed by [name])
Division Research Overhead	\$14000	
Indirect Costs (58.5%)	\$79000	
Total	\$226000	

References

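### The plan intends an unseen validation cohort, but its stated order of grouping, training and label release does not secure one

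*Combined protocol and SAP*

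**What the plan says.** The intent is clear. The Abstract says the investigators will "task the algorithms to identify subjects with clinically important VHD, as identified by a gold standard, from naïve phonocardiograms". Primary Outcome defines the result as identification of disease "by the algorithm on the device measurements from subjects in the validation set", reported as a ROC curve and as likelihood ratios "of the test at sensitivity cutoffs of 0.9, 0.95, and 0.99". Secondary Outcome says that its own, additional algorithm is built from the derivation set. Sample Size Justification treats the two cohorts as distinct: "Sample Size = 110 per group; 330 per cohort (control, AS case, MR case); 660 overall (training and validation cohorts".

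The operating rules stand in three other places of the combined protocol and SAP:

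- **Study subjects, Overview.** "These subjects will be grouped into derivation and validation cohorts sequentially, stratified by case status, so as to reach the expected sample size". The next sentence gives the timing: "Such grouping will occur after subject enrollment and data collection".
- **Justification of Critical Assumptions.** "the number needed for our derivation set is less clear; the estimates above are a conservative number". The algorithm is to be trained, with bootstrapping, whenever a further 20 cases have been enrolled. The interim performance then helps settle how large the derivation set must be.
- **Data Management Plan.** Recordings go in real time to a server run by the device company, which also coordinates the machine learning team. At training times fixed in advance, that team receives the keys that link subject identifiers to valve disease category.

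Neither the training sentence nor the key-release sentence is limited to derivation subjects. No section says when training stops, when the algorithm is frozen, or that validation keys are withheld.

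**The concern.** A validation result measures performance in new patients only if those patients played no part in fitting or tuning the algorithm. Here the split is described as coming after enrollment and data collection, while training and label release go on during enrollment. Read in that order, labels for subjects who later fall in the validation cohort can already be with the training team. The boundary between cohorts can also be settled after interim performance has been seen.

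The primary outcome is at stake. If subjects used to fit or tune the final algorithm also sit in the validation set, the ROC curve is biased upward. At the fixed sensitivities in Primary Outcome, the bias would show as too few false positives and so too high an LR+, which is the quantity the sample size is built on. Once a label has been used for training, that subject cannot be made unseen again.

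**Working it through.** **1. The plan's own figure.** Inputs from Sample Size Justification: Sn = 0.90, Sp = 0.90, n = 110 per group, 95% confidence.

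- LR+ = Sn / (1 − Sp) = 0.90 / 0.10 = 9.0.
- SE(ln LR+) = √[(1 − Sn)/(n·Sn) + Sp/(n·(1 − Sp))] = √[0.10/99 + 0.90/11] = 0.2878.
- Limits = 9.0 × exp(±1.96 × 0.2878) = 5.120 to 15.820.

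This matches the stated interval exactly. The totals also agree: 110 × 3 = 330 per cohort, and 330 × 2 = 660. The sum works only if the cohorts do not share subjects, so no stated figure is wrong. The question is whether the procedure delivers the separation that the figures assume.

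**2. The order of steps, side by side.**

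| Step | When | Limited to derivation subjects? |
|---|---|---|
| Training | Each further 20 enrolled cases | Not stated |
| Release of disease keys | Training times fixed in advance | Not stated |
| Settling the derivation number | Informed by interim results | Not applicable |
| Grouping into cohorts | After enrollment and data collection | Not applicable |
| Freeze of the algorithm | Not stated | Not applicable |

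**3. Where the training points fall.** Planned cases: 2 lesions × 110 × 2 cohorts = 440. Nominal derivation cases: 2 × 110 = 220. With AS and MR cases counted together:

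- training points if training runs to the end: 440 / 20 = 22;
- training points up to the nominal cut: 220 / 20 = 11;
- training points after it: 22 − 11 = 11.

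The plan does not say whether the 20 cases are pooled or counted per lesion. Counted per lesion, 220 cases give 220 / 20 = 11 points. Five of these (20 to 100) come before the cut at 110 and six (120 to 220) after it.

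These counts assume a sequential cut at the nominal number, AS and MR groups that fill evenly, and training that continues after derivation is full. They show how much opportunity for overlap the wording leaves. They do not measure overlap.

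**4. Room to enlarge the derivation set within 660.** Each group has 220 subjects across both cohorts. With Sn = Sp = 0.90, the lower limit is 9.0 × exp(−1.96 × √(9.111/n)), where 9.111 = 0.10/0.90 + 0.90/0.10.

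- n = 102 in validation (118 in derivation): 5.01.
- n = 101 in validation (119 in derivation): 4.996.

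The derivation set can therefore take 8 more subjects per group (118 − 110) before the planned lower limit drops below 5.

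**The case against.** The strongest reply is that the plan already separates the cohorts. Secondary Outcome builds a separate algorithm from the derivation set, in parallel with the primary one, which implies that the primary algorithm is built the same way. The sample size line uses training as the name of one of two cohorts.

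The timing sentence can also be read subject by subject, because case status is known only after that subject's echocardiogram. Grouping could then precede every training point. Interim training is said to serve the derivation number, so it would naturally use derivation subjects and end when that cohort is full. Key release is staged at times fixed in advance, the master file linking subjects sits on a separate research server, and sequential grouping limits any free choice of who is validated.

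Much of this stands. The intent is beyond doubt, partial controls exist, and on either benign reading there is no overlap. What does not stand is that the text requires one of those readings. Fixing when keys are released does not fix whose keys are released. Sequential order protects later subjects only if the boundary is settled first, and the plan lets interim results help set it.

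A reader might infer that the final algorithm will be trained on validation subjects. The documents do not support that: overlap is left possible, not prescribed. Interim models are also not the final one, and direct bias arises only if validation subjects help to fit or tune the algorithm that is finally assessed.

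A reader might also take the closeness of 5.12 to the minimum of 5 as a sign of how much leakage matters. It reflects only the planned precision. The value 5 is a sample size input and an estimate of clinical usefulness. The plan does not make it a success rule.

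**Conclusion.** The point holds as a gap between intent and procedure. Read literally, the order of grouping, interim training and key release does not secure an unseen validation cohort. It also allows the cut to be settled after labels and interim performance are known.

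Up to 11 of 22 training points could fall after the nominal 220-case cut, on the assumptions that cases are pooled, the two lesions accrue evenly, and training runs through all 440 planned cases. Any use of those later subjects in fitting or tuning the final algorithm would bias the validation ROC curve and LR+ upward. The documents give no basis for estimating by how much.

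The pilot character of the study does not remove the point, since the plan itself presents the true sensitivity and specificity as a valuable result. The passages should be reconciled before the first labels are released.

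**What to change.** Three changes of wording would close the gap.

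- **Study subjects, Overview.** Assign each subject to derivation or validation in enrollment order within stratum, once the echocardiogram category is known and before any label for that subject is released. Fix the derivation number in advance, nominally 110 per group.
- **Justification of Critical Assumptions.** Limit interim training and bootstrapping to derivation subjects. Record any change to the derivation number before further labels are released. No subject whose label was released for training moves to validation.
- **Data Management Plan.** Release keys for derivation subjects only, and withhold validation keys until the algorithm is frozen.

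Interim training and the option to revise the derivation number both remain. The cost is that validation labels cannot be used to improve the algorithm before the primary analysis. The stated LR+ interval and the total of 660 are unchanged if 110 per group remain for validation. If derivation is enlarged within 660, the interval must be restated: the lower limit is 5.01 with 102 validation subjects per group and 4.996 with 101. The plan regards its derivation number as conservative, so enlargement is the less likely direction.

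### Neither the person recording nor the quality review is masked to likely case status, so recording effort could differ between suspected cases and controls, and validation would not show it

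*Combined protocol and SAP*

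**What the plan says.** All references are to the combined protocol and SAP.

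- **Study subjects, Sampling Scheme.** Subjects are approached consecutively. In addition, "we will pre-screen subjects for a high likelihood of having AS or MR (based on indication for study and prior diagnoses" in the medical record). The scheme then speaks of selecting "their enrollment during situations where the enrollment capacity of the study coordinator is saturated". It does not say who does the pre-screen or whether that person also records.
- **Study subjects, Recruitment Strategy.** Subjects are approached while they wait for the echocardiogram. When the recording itself is made is not stated.
- **Measurements, Device Measurements.** "Recordings of the simultaneous PCG and single-lead ECG will be performed for each subject in a standardized manner": 10 seconds at each of four positions, by trained observers. The observer sees the phonocardiogram live, and "the observer will get real-time feedback on positioning of the device to maximize the quality of the recording at each position". The plan counts this as a strength: "We anticipate that this flexibility and real-time feedback will improve the generalizability of the use of the device to a real-world" clinical setting.
- **Miscellaneous, Quality control measures.** "Periodic review of the recorded data will be performed by the study PI to ensure appropriate data quality". Masking of this review to the echo grade is not mentioned.
- **Measurements, Confounders and Bias.** The algorithms are built and tested remotely after the echocardiogram, "therefore with no effect on the outcome of the gold standard". The paragraph also covers other causes of systolic murmur. It does not consider whether knowledge of the likely diagnosis could affect the recording.

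**The concern.** The index test depends on an operator. The signal that guides the observer is the one in which a murmur appears. An observer who knows from the chart, or from an echocardiogram already done, that AS or MR is likely may take more care over position than with another subject. The plan protects the reference standard from the index test. It does not protect the index test from knowledge of the likely diagnosis.

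Two things could follow. Cases could yield clearer murmurs than they would in routine use. The learning algorithm could also pick up recording quality or placement as a marker of case status. Both would carry into the validation set, because subjects are assigned to cohorts only after enrolment and data collection, from one recording process.

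At stake is whether the ROC curves and likelihood ratios apply to the use described under Significance, where the diagnosis is not yet known. The Justification of Critical Assumptions calls the true sensitivity and specificity a valuable result in itself.

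**Working it through.** **1. Is there a route from likely status to recording effort, and is it closed?**

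| Step | What the plan provides | What it leaves open |
|---|---|---|
| Knowledge before recording | Chart pre-screen on indication and prior diagnoses | No masking of the observer; no separation of pre-screener and recorder |
| Timing | Approach before the echocardiogram | Time of recording not stated |
| Discretion | Four positions, 10 seconds, training, live feedback | No acceptance criterion, attempt limit or attempt log |
| Review | Periodic, by the PI | Not stated to be masked or compared by case status |
| Cohort split | After data collection | Both cohorts share any recording bias |

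The route is open at each step, though narrowed by standardization and training.

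**2. Where would a bias show?** The Primary Outcome section sets likelihood ratios at sensitivities of 0.9, 0.95 and 0.99. Sensitivity is therefore fixed at those points. Inflated separation of cases and controls would appear as higher specificity, higher LR+ and a higher ROC curve.

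**3. The plan's own figure.** Inputs from the Sample Size Justification: Sn = 0.90, Sp = 0.90, 110 per group, 95% confidence, minimum LR+ of 5.

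Formulas (log method):
- LR+ = Sn / (1 − Sp)
- SE(ln LR+) = √[(1 − Sn)/(n₁·Sn) + Sp/(n₂·(1 − Sp))]
- limits = LR+ × exp(±1.96 × SE)

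With n₁ = n₂ = 110:
- LR+ = 0.90/0.10 = 9.00
- SE = √[0.10/99 + 0.90/11] = √(0.00101 + 0.08182) = 0.2878
- limits = 9.00 × exp(±0.5641) = 5.12 to 15.82

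This reproduces the stated 5.120–15.820. The lower limit clears the minimum by 0.12.

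**4. Illustration: Sn held at 0.90, lower specificity assumed.** Suppose the planned specificity were reached only with help from unequal recording effort. At Sp = 0.89:
- LR+ = 0.90/0.11 = 8.18
- SE = √[0.10/99 + 0.89/12.1] = √(0.00101 + 0.07355) = 0.2731
- limits = 8.18 × exp(±0.5352) = 4.79 to 13.97

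| Specificity without the artefact (assumed) | LR+ | 95% CI |
|---|---|---|
| 0.90 | 9.00 | 5.12–15.82 |
| 0.89 | 8.18 | 4.79–13.97 |
| 0.88 | 7.50 | 4.50–12.49 |
| 0.85 | 6.00 | 3.83–9.40 |

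In counts, 99 of 110 controls correctly classified gives the planned result. With 98 of 110, LR+ = 0.90/(12/110) = 8.25 and the lower limit is 4.82. These shifts are assumptions; the documents give no estimate of the effect.

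**The case against.** **The plan already standardizes.** Positions and duration are fixed and observers are trained. This stands as a reduction of the risk. It is not masking, and it sets no rule for when a recording is accepted.

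**The observer may not know the status.** A reader might infer that the pre-screener makes the recordings, or that the observer repeats them until satisfied. The documents say neither. They mention a pre-screen, a study coordinator and live feedback on position. The point rests on the absence of a safeguard, not on a stated practice.

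**Controls are not silent hearts.** A reader might infer that there is nothing to look for in a control. All subjects are referred for clinical echocardiography. Primary controls may have valve disease up to mild, secondary controls anything below moderate-to-severe, and the plan recognises other causes of systolic murmur. The pre-screen also indicates likely AS or MR, not the grade that defines a case. This stands and weakens the contrast in effort, but does not abolish it.

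**The PI review has no stated path to bias.** The documents do not say that it excludes recordings, so it is an unmasked step rather than a shown source of bias.

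**The arithmetic shows thin slack, not this bias.** That is right. Any bias of similar size would move the limit below 5. The value 5 is a planning threshold and an estimate of clinical usefulness, not a formal success test, and the study is described as partly a pilot.

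**Conclusion.** The gap is real and moderate. The plan combines a chart pre-screen for likely disease with a recording steered by live feedback, and it masks neither the recording nor its quality review. It also leaves the order of recording and echocardiogram open. The derivation–validation split cannot detect a bias common to both cohorts.

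Size and direction are not known from the documents. Inflated performance is the more plausible direction, but that is a judgement. A reader might conclude that reported sensitivity will be too high by some number of points. The documents do not support this: they give no such figure, and the planned likelihood ratios fix sensitivity.

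The illustration rests on Sn 0.90, 110 v 110, the log-method interval and an assumed one-point difference in specificity. It shows that a small artefact would be enough to move the lower limit from 5.12 to 4.79, across the plan's own minimum. It does not show that such an artefact will occur. The sample-size calculation itself is correct.

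**What to change.** Keep the live feedback and add the following to Device Measurements and Quality control measures before enrolment:

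1. Complete all recordings before the subject's echocardiogram.
2. Apply to every subject one limit on attempts per position and one signal-quality rule for acceptance that does not depend on a murmur being present.
3. Do the PI quality review by study ID, before the echo grade is linked.
4. Log attempts and rejections, and compare them by case status in the report.
5. Where existing staffing allows, have someone other than the recorder do the pre-screen and pass on names only.

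Items 1 to 4 need protocol and training wording, minor logging work and a short definition of the signal-quality rule, which the plan does not yet contain. Some retained recordings will be less polished. Item 5 is conditional because the Budget shows a single research-coordinator line and may not cover a second person's time. No change to the sample size is needed. Recording effort that was neither masked nor logged cannot be put right after enrolment.
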